10.1.2 Exploratory Endpoints

Stratum A:

 Induction of the H3.3K27M epitope-specific CTL response in post vaccine PBMCs in HLA-A2 (02:01)+ children with H3.3K27M positive gliomas other than DIPG
- Assessment of H3.3K27M infiltrates in subjects with evidence of progression that undergo tissue collection as part of their standard of care. Tumor tissue will be analyzed for H3.3K27M expression status and infiltration of H3.3K27M specific T cells
- To archive tumor and normal DNA from each subject at time of initial diagnosis along with serial blood draws following therapy to determine whether circulating tumor DNA (ctDNA) sequences in the subject's blood serve as biomarkers of tumor burden, response to therapy, or development of drug resistance.

Stratum B:

- Induction of the H3.3K27M epitope-specific CTL response in post vaccine PBMCs in HLA-A2 (02:01)+ children with H3.3K27M positive gliomas other than DIPG
- Assessment of H3.3K27M infiltrates in subjects with evidence of progression that undergo tissue collection as part of their standard of care. Tumor tissue will be analyzed for H3.3K27M expression status and infiltration of H3.3K27M specific T cells
- To archive tumor and normal DNA from each subject at time of initial diagnosis along with serial blood draws following therapy to determine whether circulating tumor DNA (ctDNA) sequences in the subject's blood serve as biomarkers of tumor burden, response to therapy, or development of drug resistance.

Stratum C:

- To determine the OS12 in HLA-A2 (02:01)⁺ children with H3.3K27 positive DIPGs and midline gliomas (excluding primary spinal cord tumors) that are treated with repeated administration of the H3.3K27M peptide and nivolumab.
- Induction of the H3.3K27M epitope-specific CTL response in post vaccine PBMCs in HLA-A2 (02:01)+ children with H3.3K27M positive gliomas including DIPG or other H3.3K27M positive midline gliomas, excluding primary spinal cord tumors.
- To archive tumor and normal DNA from each subject at time of initial diagnosis along with serial blood draws following therapy to determine whether circulating tumor DNA (ctDNA) sequences in the subject's blood serve as biomarkers of tumor burden, response to therapy, or development of drug resistance.
- To assess Quality of Life (QoL) and cognitive measures in HLA-A2 (02:01)⁺ children with H3.3K27M positive DIPG or other midline gliomas.

10.1.3 Stratification Factors

This trial will enroll into 3 strata based on disease location and treatment intervention – **Stratum A:** DIPG; **Stratum B:** any other H3.3K27M positive midline glioma, including spinal cord tumors; and **Stratum C:** DIPG and any other H3.3K27M positive midline glioma, excluding primary spinal cord tumors.

10.1.4 Design

We will enroll into the 3 strata separately: Stratum A consists of HLA-A02:01⁺ positive newly diagnosed patients with H3.3K27M positive DIPG, stratum B consists of other HLA-A02:01⁺ positive newly diagnosed patients with H3.3K27M positive gliomas that are not classified as DIPG, including spinal cord tumors and stratum C consists of subjects with HLA-A02:01⁺ H3.3K27M positive DIPG or other HLA-A02:01⁺ H3.3K27M positive midline gliomas, excluding primary spinal cord tumors. The separation of strata A and B is based on anticipation that toxicity of the vaccine and Poly-ICLC could be significantly different based on the primary tumor location. Toxicities resulting from pseudoprogression or local reaction (such as edema or inflammation) may manifest differently when tumors are located within the brainstem (as in DIPG) versus outside the brainstem, such as the spine or other part of the brain. Treatment related reaction in the brainstem may be more toxic due to a more restricted space and closer proximity to high-risk anatomic structures. The first 3 patients in each stratum will be observed at least for 6 weeks before the next set of patients are enrolled.

- If there are no RLTs in the first 3 subjects, enrollment will commence continuously within each stratum.
- If 2 or 3 RLTs occur in the first 3 subjects, accrual will be suspended and the investigator, PNOC leadership and Sponsor will make decisions regarding continuation of study accrual.
- If a RLT occurs in 1 of the first 3 patients, an additional 3 patients will be enrolled in that stratum and observed for at least 12 weeks. In this case:
 - If fewer than 2 of the first 6 patients in each stratum experience RLT with at least 12 weeks of follow-up, the remaining patients will be enrolled.
 - If a RLT occurs in ≥ 2 of the first 6 patients accrual will be suspended and the investigator, PNOC leadership and Sponsor will make decisions regarding continuation of study accrual.

If enrollment commences, all additional patients will be monitored continuously for treatment-related adverse events by the study PIs Drs. [name] and [name]. With six patients, there is an 88% probability of detecting 1 or more RLTs with an underlying rate of 30%. There is a 74% probability of detecting 1 or more RLTs with an underlying rate of 20%. If all 19 patients are enrolled in Stratum A, there is an 86% probability of detecting 1 or more RLTs with an underlying rate of 10% and a 62% probability with an underlying rate of 5%. If all 10 patients are enrolled in Strata B, there is a 65% probability of detecting 1 or more RLTs with an underlying rate of 10% and a 40% probability with an underlying rate of 5%. If all 20 patients are enrolled in Strata C, there is an 88% probability of detecting 1 or more RLTs with an underlying rate of 10% and a 64% probability with an underlying rate of 5%.

Enrollment into Stratum C will start once Strata A and B have completed accrual.

- **10.2** Determination of Sample Size and Accrual Rate
- **10.2.1** Sample Size and Power Estimate

For the primary endpoint for stratum A, we will assess the efficacy endpoint (OS12) in 19 evaluable patients with H3.3K27M positive DIPG. Prior research has shown overall survival for children with DIPG ranges from 30-40% at 12 months^{38,39}. The most recent Children's Oncology Group study that treated children newly diagnosed with DIPG with a combination of radiation therapy and temozolomide resulted

in an OS12 rate of 40% (SD \pm 6.5%)¹. Review of outcomes of DIPG patients on PNOC studies of children and young adults with newly diagnosed DIPG who received standard of care radiation therapy revealed an OS12 rate of 50% (PNOC003 - NCT02274987 and PNOC007 - NCT02960230, unpublished data). For PNOC003 patients were enrolled prior to the start of radiation therapy - similar to the COG study- and none of the enrolled patients came off study due to progression during or at completion of radiation therapy making this a reasonable control group for this study.

With a null hypothesis that OS12 is 40%, a sample size of 19 patients achieves 80% power to detect a difference of 30% using a one sided exact binominal test⁴⁰. The target significance level is 5% and the actual significance level is 3.5% with this test. If 12 or more patients are alive at 12 months, the null hypothesis that OS12 is 40% will be rejected. Patients lost to follow-up before 12 months will be considered events. OS12 will be estimated from the Kaplan-Meier method. Two-sided 95% CI will be computed based on the Greenwood's formula. If the null hypothesis is truly OS12 = 30% or OS12 = 50%, a sample size of 19 patients still achieves 80% power to detect a difference of 30%, however, the number of patients needed to reject the null changes to n = 10 or n = 14, respectively.

For the secondary endpoint for stratum C, we will assess the efficacy endpoint (OS12) in 20 evaluable patients with H3.3K27M positive DIPG or other midline gliomas, excluding primary spinal cord tumors.

In comparing outcomes to other H3K27M positive midline gliomas, OS rates similar to those for Stratum A are reported, although the reference literature is sparser for this patient population^{31,32}. Thus, similar to stratum A, a sample size of 20 patients achieves 80% power to detect a difference of 30% using a one sided exact binominal test (see above)⁴⁰.

At time of data analysis, we will use the most recent published data and PNOC enrollment data in order to determine the appropriate null rate for stratum A and stratum C.

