6.3 Regimen Limiting Toxicity (RLT)

Each patient receiving K27M/TT peptide vaccination and poly-ICLC or K27M/TT peptide vaccination and poly-ICLC in combination with nivolumab will be evaluable for safety. The safety parameters include all laboratory tests and hematological abnormalities, physical findings, and spontaneous reports of adverse events reported to the investigator by patients.

RLT includes any of the following events that occur during the first 8 vaccine doses (the entirety of the time from the 1st vaccine administration through the 8th vaccine administration) and up to 30 days after the 8th vaccine administration and are considered either possibly, probably, or definitely to the vaccine:

- Any grade 2 or greater autoimmune reaction.
- Any grade 3 or greater hematologic or non-hematologic toxicity with the exception of lymphopenia.
- Any life-threatening event.
- Any other unexpected Grade 2 or greater neurological deficit, which is possibly, probably, or definitely related to the vaccine therapy that does not respond within 21 days trial of 0.3mg/kg day dexamethasone or equivalent (max 12mg/day) or Avastin equivalent (10mg/kg every 2 weeks for a maximum of 3 doses)

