In the subject line: "SAE: Patient PNOC ID" (e.g. "SAE: PNOC007-1")

In the body of the email: registration number, weight, study drug dose with frequency and route, dates of use, site PI's attribution, outcome (ongoing, resolved etc.). Please also provide a comprehensive event description (including whether event subsided when treatment was halted, and if re-introduction was attempted and if so, if event recurred), pertinent labs or tests with dates, concomitant medications, and any other relevant history. The lot number or other unique information about the study drug should also be provided. Any information that is not available at the time of the initial notification must be provided as soon as possible on an ongoing basis until the SAE and all queries have been resolved.

Site IRB: Each PNOC site is also responsible for following their own IRB guidelines for reporting SAEs.

All Serious Adverse Events (SAEs) that occur following the subject's written consent to participate in the study through 100 days of discontinuation of dosing must be reported to PNOC, whether related or not related to study drug.

See additional details for SAE reporting in Section 9.9

SAE Data Entry in AE CRF:

All SAEs must also be entered into the AE CRF for that Cycle (Subject Console > Forms by Status/Forms by Visit). This entry must take place within 10 days of the last day of the Cycle in which the SAE occurred, or as soon as possible in the case of an SAE that was discovered late. Please reference the "PNOC SAE Reporting and Entry" in SharePoint for more information.

SAE Deviations:

If the protocol procedures around SAEs are not followed (e.g. reporting timelines or dose modifications), a Deviation may also need to be entered in OnCore (Subject Console > Deviation Tab on left)/the Advarra EDC. Please reference the "PNOC Deviation Reporting Guidelines" in SharePoint for more information.

Email notification to PNOC operations office **within one business day** of first PI awareness.

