9.10 PNOC Reporting

9.10.1 Reporting to the UCSF Data and Safety Monitoring Committee

If a death occurs during the treatment phase of the study, or within 30 days after the last administration of the study drug(s), and is determined to be related either to the investigational drug or to any research related procedure, the Study Chair and the PNOC Operations Office must be notified by the member institution within 1 business day. The Study Chair or the PNOC Operations Office must then notify the UCSF DSMC Chair, or qualified alternate, within 1 business day of this notification. The contact may be by phone or e-mail. Each participating site will follow their institutional reporting guidelines to institutional DSMC.

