10.3 Interim Analyses and Stopping Rules

The study will be monitored by Drs. [name] and [name] and the PNOC Operation's office on a weekly basis including a review of all adverse events and deviations entered within Advarra[®] in concordance with the PNOC requirements for phase 1/2 clinical trials. The toxicity monitoring rules for the following events will be applied to all patients treated in the study. The regimen limiting toxicity (RLT) will be based on the tolerability observed following the vaccine doses following radiation therapy.

RLT includes any of the following events that occur during or following any vaccine given.

- Any grade 2 or greater autoimmune reaction.
- Any grade 3 or greater hematologic or non-hematologic toxicity with the exception of lymphopenia.
- Any life-threatening event.
- Any other unexpected Grade 2 or greater neurological deficit, which is possibly, probably, or definitely related to the vaccine therapy that does not respond within 21 days trial of 0.3mg/kg day dexamethasone or equivalent (max 12mg/day) or Avastin or equivalent (10mg/kg every 2 weeks for a maximum of 3 doses)

In addition to the stopping rules specific to the design detailed above, all patients will be monitored continuously for treatment-related adverse events by the study PIs Drs. [name] and [name].

Sequential boundaries will be used to monitor the RLT rate. The accrual will be halted if excessive numbers of RLTs are seen, that is, if the number of RLTs is equal to or exceeds b_n out of *n* patients with full follow-up (see table below). This is a Pocock-type stopping boundary that yields the probability of crossing the boundary at most 0.0475 when the rate of RLT is equal to the acceptable rate of 0.20.

For example, in Stratum A, the trial will be stopped if the number of RLTs is equal to or exceeds b_n out of *n* patients with completed follow-up.

Number of Patients, n 1 2 3 4 5 6 7 8 9 10 11 12 13 14 15 16 17 18 19

Boundary, b_n - - 34445556 6 6 7 7 7 8 8 8 9

This boundary is equivalent to testing the null hypothesis, after each patient, that the event rate is equal to 0.2, using a one-sided level 0.021430 test.

θ	φ*	E[Y]	SD[Y]	E[N]	SD[N]	E[Y/N]	SD[Y/N]
0.20	0.0475	3.70	1.62	18.51	2.39	0.21	0.13
0.30	0.2248	5.08	1.55	16.92	4.44	0.34	0.18
0.40	0.5327	5.60	1.49	14.00	5.76	0.48	0.20
0.50	0.8151	5.30	1.54	10.59	5.62	0.60	0.20

Definitions:

Y = the number of events, random, between 0 and N N = the number of patients, random, between 1 and K

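### The accrual rules count RLTs without regard to severity, so one treatment-related death triggers neither rule, and no section makes further Stratum C enrolment conditional on review of the death

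*Combined protocol and SAP*

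**What the plan says.** **Gate (10.1.4).** The opening hold is "The first 3 patients in each stratum will be observed at least for 6 weeks before the next set of patients are enrolled". With no RLT in those 3, enrolment becomes continuous. With exactly one, "If a RLT occurs in 1 of the first 3 patients, an additional 3 patients will be enrolled in that stratum", observed for at least 12 weeks; the rest of the stratum follows if fewer than 2 of the 6 have an RLT. The two suspension triggers are "If 2 or 3 RLTs occur in the first 3 subjects, accrual will be suspended" and, after expansion, "If a RLT occurs in ≥ 2 of the first 6 patients accrual will be suspended". Decisions after a suspension lie with the investigator, consortium leadership and sponsor. The DSMC is not named.

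**Boundary (10.3).** "The accrual will be halted if excessive numbers of RLTs are seen", measured by the RLT count among patients with full follow-up. The printed boundary has no value at 1 or 2 patients, then requires 3 RLTs in 3, 4 in 4 to 6, 5 in 7 to 9, 6 in 10 to 12, 7 in 13 to 15, 8 in 16 to 18 and 9 in 19.

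**RLT definition (6.3).** A related death has no category of its own. It enters through "Any grade 3 or greater hematologic or non-hematologic toxicity with the exception of lymphopenia", grade 5 being death (9.6). The event must be at least possibly related to the vaccine and occur no later than 30 days after the 8th vaccine dose. Section 10.3 lists the same event types but covers events during or after any vaccine given.

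**Death reporting.** Sections 9.10.1 and Appendix D require prompt notice to the DSMC Chair if a death occurs on treatment or "within 30 days after the last administration of the study drug(s), and is determined to be related either to the investigational drug" or to a research procedure. Section 9.9 has a wider window: all SAEs "through 100 days of discontinuation of dosing must be reported to PNOC". Appendix D also acknowledges that the Study Chair or Operations Office may halt enrolment for safety.

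**The concern.** A related death carries the same weight in both rules as a related grade 2 autoimmune reaction. The question for a safety design is whether a death can occur and the next child be enrolled with no prior decision that this is acceptable. On the written rules it can.

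The point is live for Stratum C only. Sections 1.3 and 5.1.5 report that the 19 Stratum A and 10 Stratum B patients have been treated. Stratum C adds nivolumab, and the abstract describes the study as the first of this peptide alone and with PD-1 inhibition. The RLT wording in 6.3 ties attribution to the vaccine, so some Stratum C deaths might not enter the count at all.

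**Working it through.** **1. The plan's own figures reproduce.** An exact patient-by-patient binomial recursion over the printed boundary (n = 3 to 19) gives crossing probabilities of 0.0475, 0.2248, 0.5327 and 0.8151 at RLT rates of 0.20, 0.30, 0.40 and 0.50, as printed in 10.3. Each boundary value is the smallest count whose exact upper tail at 0.20 is at or below 0.021430. The Stratum C detection probabilities in 10.1.4 also reproduce: 1 − 0.90^20 = 0.878 and 1 − 0.95^20 = 0.642. The issue is therefore not an arithmetic error.

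**2. Smallest count that acts.** Gate: 2 RLTs. Boundary: 3 RLTs. One RLT of any grade triggers neither.

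**3. A fatal sole RLT in the first 3.** Let p be the total RLT rate and f the fatal part of it. The documents give neither for the combination; both are assumptions.

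- P(exactly one RLT in 3, and it is fatal) = 3f(1 − p)².
- f = 1%: 3 × 0.01 × 0.80² = 0.019 at p = 20%; 3 × 0.01 × 0.90² = 0.024 at p = 10%.
- f = 5%: 0.096 and 0.122.
- Given that event, the gate opens to all remaining patients if the next 3 have no RLT: 0.80³ = 0.512 or 0.90³ = 0.729.

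**4. All of Stratum C.** Inputs: 20 independent patients, with gate and boundary both applied. Outcomes are taken as known at once, which favours the plan because 10.3 counts only patients with full follow-up. The boundary is printed to n = 19. The same nominal level gives 9 at n = 20, since P(X ≥ 9) = 0.010 and P(X ≥ 8) = 0.032 at a rate of 0.20. The recursion tracks RLTs, deaths and RLTs in the first 3. P(any related death) = 1 − (1 − f)^20.

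| f | p | Any related death | Death and never suspended | Share of trials with a death never suspended | Two or more deaths, never suspended |
|---|---|---|---|---|---|
| 1% | 20% | 0.182 | 0.113 | 62% | 0.9% |
| 1% | 10% | 0.182 | 0.153 | 84% | 1.3% |
| 5% | 20% | 0.642 | 0.418 | 65% | 15% |
| 5% | 10% | 0.642 | 0.558 | 87% | 21% |

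Across all trials, with or without a death, the never-suspended share is 70% at p = 20% and 91% at p = 10%. A death therefore makes suspension only slightly more likely than it already was.

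**5. Which deaths count.** The 8th dose is at week 21, so the window in 6.3 closes at about week 25 (21 weeks plus 30 days). Stratum C may be treated to week 96. A death at week 40 is outside 6.3 but, if it follows a vaccine dose, inside the wording of 10.3. A death attributed only to nivolumab does not meet the attribution condition in 6.3, while the opening wording of 10.3 sets none. The two sections give different counts for the same events.

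**The case against.** The strongest reply is that the plan has far more safety review than its accrual rules show. Every SAE reaches the consortium within one business day (9.9). The study team is alerted within one more business day and must rule on relationship and expectedness, and unexpected fatal suspected reactions go to the FDA within 3 business days of that determination (9.10.3). The DSMC reviews SAEs on an ongoing basis and meets every six weeks (9.8). Adverse events are reviewed weekly (10.3). The 6- and 12-week holds give time for discussion. This stands: a reader might infer that a death could pass without review, or that the DSMC Chair notice is the only rule for fatal events, and the documents contradict both. What remains is that none of these reviews is a condition for the next enrolment, and once continuous enrolment opens no hold applies.

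Second, the 30-day and 100-day windows serve different purposes. A reader might infer that related deaths on days 31 to 100 go unnoticed. They do not: they remain one-business-day SAEs and enter DSMC review. Only the direct notice to the DSMC Chair lapses.

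Third, nothing in the documents points to a high death rate. Section 5.1.5 reports one RLT in 29 vaccine patients, and 1.1 reports no grade 3 or higher systemic toxicity in the 26-child peptide trial and good paediatric tolerability of nivolumab. None of these is combination data, but they are why the 1% rows are shown. A reader might also take 10.1.4 as predicting worse toxicity in the brainstem. It says only that this may occur, as the reason for separating strata A and B, and 1.3 cites favourable safety in both when combining these tumour types in Stratum C.

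**Conclusion.** The gap is real but narrow. Review of a related death is required and a discretionary halt exists. What is missing is any provision that makes further enrolment wait for the review, or that gives the DSMC a stated part in resuming. One related death triggers neither accrual rule. If it is the sole RLT in the first 3, three more children are enrolled after the 6-week observation, and the rest may follow after 12 weeks if no second RLT occurs.

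Under the assumed rates, 62% to 87% of Stratum C trials with a related death are never suspended. This barely depends on the death rate and largely restates that the rules act on counts. The absolute risk does depend on it: two or more related deaths without suspension has a chance of about 1% at a 1% fatal rate and 15% to 21% at 5%. These figures assume independent patients and immediate knowledge of outcomes. They illustrate how the rules behave and do not forecast mortality.

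The difference between 6.3 and 10.3 is a separate inconsistency that could leave some Stratum C deaths uncounted. Overall this is a cheap improvement to accrual governance, and no figure in the plan needs correcting.

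**What to change.** For Stratum C:

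- The sponsor and the DSMC should state in 10.1.4 and 10.3 how a death at least possibly related to any study agent affects accrual. Further enrolment should be conditional on documented review by the existing DSMC, whatever the RLT count. The details of the rule are theirs to set.
- Reconcile the RLT definitions in 6.3 and 10.3, both the time window and the attribution, including events attributed to nivolumab.
- As minor harmonisation, align the 30-day DSMC Chair notice (9.10.1, Appendix D) with the 100-day SAE window (9.9, 9.10.4).

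The cost is a short amendment, using a committee that already receives the SAEs. The downside is a possible short accrual pause per related death, including some deaths later judged to be due to tumour. If review waits for a scheduled meeting, the six-weekly cycle implies up to about 6 weeks; review between meetings would shorten it.

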Safety update from PNOC 007 (phase 1) cutoff date September 8, 2020: We have shown that treatment with the vaccine and poly-ICLC is safe in children with DIPG (n=19) as well as other midline gliomas including spinal cord tumors (n=10), as of September 8, 2020. With this current amendment, we will test the safety and efficacy of combined therapy of K27M/TT and poly-ICLC with nivolumab. Our hypothesis is that the combination therapy will be more effective compared to vaccine administration alone. We will combine DIPG and other midline glioma in one combined strata given our current experience that supports a favorable safety profile for both Strata A and B and that recent studies have shown similar outcomes for these entities. However H3K27 mutant spinal cord tumors seem to have significantly worse outcome and to date we have very limited safety data in this patient population with single agent vaccine (n=2) and therefore we will exclude these from Stratum C 31,32 .

2 Objectives of the Study

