10.2.2 Accrual estimates

This study aims to enroll 19 children with H3.3K27M positive DIPG (Stratum A), 10 children with H3.3K27M positive glioma, other than DIPG, including spinal cord tumors (Stratum B) and 20 children with H3.3K27M positive DIPG or other midline gliomas, excluding primary spinal cord tumors (Stratum C). Eligible patients need to test positive for the HLA-A02:01⁺ to be eligible. Based on our previous study, we anticipate that about 40 children with DIPG and 40 children with other gliomas will need to be screened to meet accrual goals¹⁴. We anticipate that most of the PNOC sites will open this study and that we will be able to screen 2-3 potentially eligible patients per month which would allow us to accrue at least one patient per month. To date, we have enrolled an average of 1.4 patients/month on the phase 1 portion of PNOC007 with 14 PNOC sites actively accruing. To date, enrollment has been similar between the strata. Therefore, we anticipate that enrollment onto Strata A and B will be completed in approximately two years. We anticipate that Stratum C will follow a similar pattern, taking up to 2 years for enrollment.

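### The 50% OS12 given for PNOC patients after standard radiation pools in this trial's own DIPG patients, and section 10.2.1 leaves it open for that figure to become the Stratum A null at analysis

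*Combined protocol and SAP*

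**What the plan says.** Section 10.2.1 (Sample Size and Power Estimate) offers three reference points for 12-month survival in DIPG: a literature range of 30% to 40%, a Children's Oncology Group study at 40%, and the consortium's own experience. The last is introduced as a "Review of outcomes of DIPG patients on PNOC studies of children and young adults with newly diagnosed DIPG who received standard of care radiation therapy", which "revealed an OS12 rate of 50% (PNOC003 - NCT02274987 and PNOC007 - NCT02960230, unpublished data"). The section then argues that PNOC003 is a reasonable control group. It makes no such argument for PNOC007 and gives no separate rate, patient count or interval for either study.

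Other sections identify PNOC007 as this protocol:

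- Section 1.3 carries a "Safety update from PNOC 007 (phase 1) cutoff date September 8, 2020" and reports that "treatment with the vaccine and poly-ICLC is safe in children with DIPG (n=19") and in ten children with other midline gliomas. These are the sizes of Strata A and B.
- Section 10.2.2 reports this trial's own accrual: "To date, we have enrolled an average of 1.4 patients/month on the phase 1 portion of PNOC007".
- Section 9.9 uses a PNOC007 number as the example subject ID in the SAE e-mail instruction.

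The formal Stratum A test in 10.2.1 has a null of 40%, is one-sided exact binomial, and rejects at 12 or more of 19. For true nulls of 30% or 50% the section adds that "the number of patients needed to reject the null changes to n = 10 or n = 14". Its last sentence says that the null for Strata A and C will be settled at the time of analysis from the latest published data and PNOC data.

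**The concern.** A reference rate for a single-arm test should come from patients who did not receive the treatment under test. The only description of the pooled PNOC group is that it had standard radiation. Section 3.2.1 requires that of every Stratum A patient, so the description removes no vaccinated child, and no unvaccinated PNOC007 subgroup is mentioned anywhere.

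If the pooled rate, or an update of it, becomes the null, the tested arm helps to set its own benchmark. A helpful vaccine would raise the bar, and a harmful one would lower it. This is separate from the question of when the null is chosen: a pooled 50% fixed in advance would contain the same patients. What is at stake is the primary efficacy conclusion for Stratum A. With 12 or 13 survivors the trial rejects a 40% null but not a 50% null.

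**Working it through.** **Inputs from section 10.2.1.** N = 19; null 40%; target difference 30 points; one-sided exact binomial test at a 5% target level; cut-offs 12, 10 and 14 for nulls of 40%, 30% and 50%.

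**Step 1: reproduce the plan.** Alpha = P(X ≥ r | 19, null); power = P(X ≥ r | 19, null + 0.30).

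| Null | Cut-off r | Alpha at r | Alpha at r − 1 | Power at null + 30 points |
|---|---|---|---|---|
| 40% | 12 | 0.0352 | 0.0885 | 0.818 |
| 30% | 10 | 0.0326 | 0.0839 | 0.814 |
| 50% | 14 | 0.0318 | 0.0835 | 0.837 |

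The stated 3.5% level, the 80% power (as at least 80%) and all three cut-offs are confirmed.

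**Step 2: effect of changing only the null.** Hold the true OS12 at the design target of 70%:

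- null 40%: P(X ≥ 12 | 19, 0.70) = 0.818
- null 50%: P(X ≥ 14 | 19, 0.70) = 0.474

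The difference, 0.818 − 0.474 = 0.344, is the chance of 12 or 13 survivors, where the two nulls give opposite conclusions.

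**Step 3: how far pooling could move a reference rate (assumed figures).** The documents give neither component rate and no PNOC003 count. Assume m PNOC003 patients with OS12 of 40%, and 19 vaccinated PNOC007 patients with OS12 of v:

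pooled rate = (19 × v + m × 0.40) / (19 + m)

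| Assumed vaccinated OS12, v | m = 19 | m = 50 |
|---|---|---|
| 30% (harm) | 35% | 37% |
| 40% (no effect) | 40% | 40% |
| 50% | 45% | 43% |
| 60% | 50% | 46% |
| 70% | 55% | 48% |

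For example, with v = 70% and m = 50: (13.3 + 20) / 69 = 0.483.

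**Step 4: read a pooled 50% backwards.** Let w be the PNOC007 share of the pool. The implied PNOC003 rate is (0.50 − w × v) / (1 − w).

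| v | w = 0.25 | w = 0.50 |
|---|---|---|
| 40% | 53.3% | 60.0% |
| 50% | 50.0% | 50.0% |
| 60% | 46.7% | 40.0% |
| 70% | 43.3% | 30.0% |

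The printed 50% is therefore compatible with a PNOC003 rate below, at or above 50%.

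**The case against.** The strongest reply is that the 50% is not the null. The formal null is 40%, which matches the Children's Oncology Group rate and owes nothing to PNOC007. This stands: the 12-of-19 rule is unaffected as long as the null stays at 40%. The point matters only because the last sentence of 10.2.1 allows the null to be reset with PNOC data.

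Some stronger readings are tempting, and the documents do not support them:

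- *The 14-of-19 cut-off is itself contaminated.* It is binomial arithmetic for any 50% null. The section sets 30% and 50% on either side of 40% and does not cite the PNOC review for that row.
- *Pooling hides a real vaccine effect.* That holds only if the vaccine helps. If it harms, the pooled null is too low and the test too lenient. If it does nothing, vaccination adds no bias.
- *The vaccine produced the 50%.* Step 3 shows that it could have, under assumed inputs, and not that it did.
- *The design loses its planned power.* The 47% is for a 20-point difference (50% to 70%). The plan claims 80% for a 30-point difference, and at 50% against 80% the power is 84%.
- *PNOC003 alone is an untreated rate.* The documents do not say what PNOC003 patients received besides radiation.

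It is also an inference, though the natural one, that the PNOC007 patients reviewed are the vaccinated Stratum A children. For Stratum C, vaccine-alone patients can be a proper comparator, since section 1.3 hypothesises that the combination does better than vaccine alone.

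**Conclusion.** The concern holds in limited form. A figure presented as the outcome after standard radiation includes patients of this trial, very probably vaccinated ones, and the plan as written allows it to inform the Stratum A null. The printed primary test is clean.

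The bias cannot be sized or signed from the documents. With PNOC003 assumed at 40% and between 50 and 19 PNOC003 patients, the pooled rate would be 43% to 45% for a vaccinated OS12 of 50%, 46% to 50% for 60%, and 48% to 55% for 70%. It would fall below 40% if vaccinated children did worse. What does not rest on those assumptions is the consequence of moving the null from 40% to 50%: a cut-off of 14 instead of 12, and power at a true OS12 of 70% of 47% instead of 82%. This should be corrected before the null is settled; it does not invalidate the design.

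**What to change.** In section 10.2.1:

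1. Report the PNOC003 OS12 on its own, with the number of patients, its interval and the treatment they received besides radiation, so that a reader can judge whether it is a fair control. If the pooled 50% is kept, say that it includes patients of this trial.
2. State that no PNOC007 patient contributes to any null rate used to test Stratum A, and apply this expressly to the closing sentence on setting the null at analysis.
3. If vaccine-alone patients serve as a reference for Stratum C, present them separately as a vaccine-alone comparator and not as a standard-radiation rate.

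The cost is one re-tabulation of data that the plan cites as the consortium's own, and a few sentences. Sample size, data collection and the 12-of-19 rule do not change. The drawback is that a PNOC003-only rate rests on fewer patients and is less precise, which its interval will show.
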